### **Recruitment Documents**

For all VNS Health Total member and family care partner recruitment documents, we will use a patient-facing title (“Improving Patient Comfort and Care with Data”) for the study to make it more accessible and understandable to these potential participants.

### **Aims 1 – Telephone script recruitment (VNS Health Total members, FCP and PC team members)**

*Greet person politely.*

*Introduce yourself and organization.*

*Ask to speak with person of interest.*

*Emphasis the purpose of the study:*

[PC team member:] The purpose of the study is to improve the way we use health records and data to connect people with additional support services such as palliative care.

And/or

[VNS Health Total member, FCP:] Learn more about member interest in palliative care and improve how we explain our programming to people.

[VNS Health Total member, FCP:] *Explain that we are contacting them because they or their family member decided not to participate in palliative care in the last year or you provided support to VNS Health Total's palliative care team.*

Ask if they would you like to hear more about the second part of the study?

*Let them know that their decision whether or not to participate will not affect their relationship {or employment} with VNS Health or Rutgers*

*If YES, continue.*

*If NO, thank the person for their time.*

*Explain what study participation involves:*

- 30-60-minute interview or focus group to answer questions about
  - [PC team member:] how you use information from electronic health record data to refer enrollees to additional support programs.  
OR
  - [VNS Health Total member/FCP:] you will be asked about your interest in and experience with additional support programs that your Medicare advantage plan may provide. Your responses will be used to improve how services and programs are explained to others in the future.
- May also be asked to participate in a second 30-60-minute interview or focus group to provide feedback on informational materials we develop from your and others' feedback.
- Brief survey to provide demographic information and knowledge of palliative care (for VNS Health Total member/FCP) or experience with VNS Health algorithm (for PC team member)

*Explain how study will be conducted:*

- By VNS Health and Rutgers University
- At VNS Health headquarters, {PC team members: during IDT meetings}, by telephone, or by secure videoconference at your convenience.
- Focus groups and interviews take from 30-60 minutes (1-2 hours in total).
- Questions will focus on:
  - [PC team member] how you assess individuals as eligible for palliative care, reasons for refusal of palliative care, how health record data could be presented in a way that is useful for determining palliative care eligibility.  
OR
  - [VNS Health Total member/FCP] knowledge of palliative care, attitudes towards it, and reasons for refusing palliative care [FCP for their loved one].
- Surveys will take 10 minutes and be conducted online via a secure link or by telephone.
- Compensation: \$75 for each round of feedback you provide during interviews or focus groups, up to \$150.

Do you have any questions?

*Answer all questions.*

Are you interested in participating?

*If YES, confirm contact information for mailing/emailing informed consent and schedule time to review it.*

*If NO, thank the person for their time.*

#### **Aim 1 – Participant email/letter recruitment (VNS Health Total Members, FCP and PC team members)**

Subject: Research Study

Dear [Colleague / name of participant]:

We are contacting you to ask for your participation in an NIH-funded research study to improve the way we use health records and data to connect people with additional support services such as palliative care. The study is called - Improving Patient Comfort and Care with Data. We will be asking about your knowledge of palliative care, attitudes towards it, and reasons for refusing palliative care for [you/your loved one].

The study will be conducted by VNS Health and Rutgers University at VNS Health headquarters, {during IDT meetings}, by telephone, or by videoconference at your convenience and consist of 1 or 2 30-60-minute sessions. You will be compensated \$75 for each session. If you are interested in participating, please reply to this email, or email or call [research assistant] at [email, phone number]. A research assistant may also follow up with you by phone to ask about participation.

This study is confidential, and participation is entirely voluntary. Your decision whether or not to participate will not affect your relationship {or employment} with VNS Health or Rutgers. Your response is an invaluable part of our research and will help us better understand how to improve care, including for people with dementia and their families. If you have any questions or comments about this work, please call or email at [phone number] [contact].

Thank you for your consideration.

Sincerely,  
[name]

IRB# [IRB #]

NOTE: Language in {} will be included for CBPC team members only.

**Aim 2 – Telephone script recruitment (VNS Health Total members, FCP and PC team members)**

*Greet person politely.*

*Introduce yourself and organization.*

*Ask to speak with person of interest.*

*Thank them for their prior participation in interview or focus group. (If they are recruited from Aim 1)*

*Let them know we are ready for the second step of the study and are reaching out to see if they are willing to help us out.*

*Emphasis the purpose of the study:*

[PC team member:] The purpose of the study is to improve the way we use health records and data to connect people with additional support services such as palliative care. Your responses will be used to improve how palliative care services and programs are explained to others in the future.

And/or

[VNS Health Total member, FCP:] Learn more about member interest in palliative care and improve how we explain our programming to people.

*Ask if they would you like to hear more about the second part of the study?*

*Let them know that their decision whether or not to participate will not affect their relationship {or employment} with VNS Health or Rutgers*

*If YES, continue.*

*If NO, thank the person for their time.*

*Explain what study participation involves:*

- 30-60-minute interview or focus group to provide feedback on informational materials we develop from your and others' feedback.

*Explain how study will be conducted:*

- By VNS Health and Rutgers University
- At VNS Health headquarters, {PC team members: during IDT meetings}, by telephone, or by videoconference at your convenience.
- Focus groups and interviews take from 30-60 minutes.
- Participants will also be asked to complete a brief questionnaire with demographic information and their knowledge of palliative care.
- The questionnaire can be completed online via a unique link sent to their email or by telephone with study personnel.
- Compensation: \$75

Do you have any questions?

*Answer all questions.*

**Aim 2 – email/letter recruitment (VNS Health Total Members, FCP and PC team members)**

Subject: Research Study

Dear [Colleague / name of participant]:

Thank you again for participating in the interview portion of our research study at VNS Health and Rutgers to improve the way we use health records and data to connect people with additional support services such as palliative care.

We are reaching out because it is time for the second part of the study to provide feedback on informational materials to improve how palliative care is explained to eligible individuals.

The study will be conducted by VNS Health and Rutgers University at VNS Health headquarters, {during IDT meetings}, by telephone, or by videoconference at your convenience and will last about 30-60 minutes. You will be compensated \$75 as a thank you for your time. If you are interested in participating, please reply to this email, or email or call [research assistant] at [email, phone number]. A research assistant may also follow up with you by phone to ask about participation.

This study is confidential, and participation is entirely voluntary. Your decision whether or not to participate will not affect your relationship {or employment} with VNS Health or Rutgers. Your response is an invaluable part of our research and will help us better understand how to improve care, including for people with dementia and their families. If you have any questions or comments about this work, please call or email at [phone number] [[contact]](mailto:[contact])

Thank you for your consideration.

Sincerely,  
[name]

IRB# [IRB #]

NOTE: Language in {} will be included for CBPC team members only.

**Aim 3 –email/letter recruitment (PC team members)**

Subject: Research Study

Dear [Colleague / name of participant]:

[Thank you again for participating in the interview portion of our research study at VNS Health to develop informational materials about palliative care.] We are ready to implement the materials and are reaching out to see if you are interested in continuing to help with this project.

You will be asked to participate in completing three 5–10-minute surveys to answer questions about your experience using the informational materials to tell eligible individuals and their family members about palliative care.

The study will be conducted by VNS Health and Rutgers University at VNS Health headquarters, {during IDT meetings}, by phone, by teleconference, or electronically at your convenience and will last about 15-30 minutes over three survey sessions. You will be compensated \$25 for each survey you complete. If you are interested in participating, please reply to this email, or email or call [research assistant] at [email, phone number]. A research assistant may also follow up with you by phone to ask about participation.

This study is confidential, and participation is entirely voluntary. Your decision whether or not to participate will not affect your relationship {or employment} with VNS Health or Rutgers. Your response is an invaluable part of our research and will help us better understand how to improve care for people with dementia and their families. If you have any questions or comments about this work, please call or email at [phone number] [[contact]](mailto:[contact])

Thank you for your consideration.

Sincerely,  
[name]

IRB# [IRB #]

NOTE: Language in {} will be included for CBPC team members only.

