**Measurements.** All measures will be collected by study research team members via phone call or electronic survey. All participants will be assessed on the measures listed in Table 1 (see Appendix for more details). Aim 1 and 2 participants will be compensated \$75 each time they participate, up to \$150. Aim 3 CBPC team member participants will be compensated \$25 each time they complete the feasibility and acceptability surveys, up to \$75.

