**Table 1.**

Domain	Proposed measure (items)	Aims	Schedule	Participants
Demographic and Health Information	Age, sex, race, ethnicity, education level, perceived discrimination in healthcare encounters (FCP only), relationship to VNS Health Total member (FCP only), role on CBPC team (CBPC team members only), etc.	1-2	Baseline (Aim 1)	VNS Health Total members, FCP, CBPC team members, research/content experts (Aim 2 only)
	Age, sex, race, ethnicity, date of CBPC eligibility determination, date of CBPC refusal, diagnoses, triggering events	3	As extracted from electronic health record for pilot clinical trial analysis	VNS Health Total CBPC-eligible members
Knowledge of Palliative and Hospice Care	Palliative Care Knowledge Survey  additional questions on palliative care knowledge and attitudes 9/26/2025 8:41:00 PM	1-2	Baseline (Aim 1), following feedback on intervention materials (Aim 2)	VNS Health Total members, FCP
Intervention Development	Interview guides with questions about palliative care experiences, knowledge, barriers to participation in CBPC, including 5 rights framework (Aim 1); and user-centered design questions to solicit feedback on intervention materials (Aim 2)	1-2	1-time interview for Aim 1. 1-time think aloud session for Aim 2	VNS Health Total members, FCP, CBPC team members, research/content experts (Aim 2 only)
Intervention Feasibility and Acceptability	PC team member reports of use of intervention	3	1, 3, and 6 months into intervention delivery (Aim 3)	CBPC team members
	End-User Satisfaction Survey 	1, 3	Baseline (Aim 1); 1, 3, and 6 months into intervention delivery (Aim 3)	CBPC team members
Primary Endpoint	Number and rate of CBPC refusals (denominator=number of CBPC-eligible individuals)	3	As extracted from electronic health record for pilot clinical trial analysis	VNS Health Total CBPC-eligible members

**Data Collection Protocol.** Survey responses for Aims 1-3 will be collected in two ways: online or by telephone. Whenever possible, participants will be sent surveys to their preferred emails via REDCap, a password protected, HIPAA compliant data management system. Survey links will be unique to study

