*Retention.* To engage CBPC team members throughout the course of the intervention, we will present the informational materials at interdisciplinary team (IDT) and other team meetings prior to their introduction into clinical practice. We will also solicit feedback on introducing the intervention to the CBPC team members from the CBPC leadership team. Additionally, as part of the intervention development process, we will solicit feedback from CBPC team members about the best way to make the informational materials available and accessible to them. We will check in with CBPC team members monthly in order to ascertain how intervention use is progressing, troubleshooting issues, and responding to CBPC team member concerns regarding material content and or accessibility.

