## **8. DATA TO BE EMPLOYED**

Please see Table 1 (above) and Appendix for data collection instruments at the end of the document. Data collection procedures will be conducted by trained research staff and done in-home, at VNS Health headquarters, at Rutgers University, by phone, by videoconference or online surveys as outlined in the protocol above. Data will be collected by research staff or online questionnaires and entered into and stored in a HIPAA compliant database such as REDCap.

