**Aim 3.** Conduct a pre-post trial to determine the feasibility and acceptability of the materials and using them in existing clinical workflows for their impact on CBPC enrollment for PLwD and end-user satisfaction. Risks to study participants are minimal for VNS Health Total members. There is no anticipated risk resulting from providing additional information about benefits of CBPC. However, participants may experience stress if they have previously refused palliative care and are being reintroduced to the service again. It is worth noting, however, that the study does not change the current procedure for identifying and approaching individuals who previously were offered palliative care and become eligible for it again. The study only changes the information about palliative that is provided to these individuals, while remaining consistent with current standards of care. We do anticipate that VNS Health Total members and FCP may gain a better understanding of potential CBPC benefits and increased support provided by CBPC for individuals who accept the service. For CBPC team members we anticipate no risk. However, they may benefit from having additional resources and information about CBPC to make it easier for them to explain CBPC to eligible individuals.

**Aims 1-3.** All study subjects can refuse to answer any questions or to discontinue study participation at any time. As always, there is the possibility that participant confidentiality will be breached. We will take steps to minimize this possibility and protect participant confidentiality as outlined in the following section. The potential benefits of the study include the individualized materials on the benefits of palliative care that will be created, potentially benefitting VNS Health Total members and FCP, particularly of PLWD, by promoting and increasing enrollment in palliative care. Additionally, this research will generate generalizable knowledge essential to improving uptake of palliative care by VNS Health Total members, including PLWD, and their family members and inform VNS Health how they might better implement palliative care promotion processes within their care system.

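### The Aim 3 staff letter offers team meetings as a setting for the satisfaction and use surveys, in conflict with the online-or-telephone rule and with no stated privacy safeguard

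*Combined protocol and SAP*

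**What the plan says.** The Aim 3 recruitment letter (Section 5, Recruitment Documents) asks team members to complete three short surveys about using the informational materials. It offers this "at VNS Health headquarters, {during IDT meetings}, by phone, by teleconference, or electronically at your convenience" and says that it "will last about 15-30 minutes over three survey sessions". The text in braces is live, because the letter goes to team members and closes with "NOTE: Language in {} will be included for CBPC team members only".

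Three other places state how data are collected:

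- Section 3, Measurements: "All measures will be collected by study research team members via phone call or electronic survey".
- Data Collection Protocol, directly after Table 1: "Survey responses for Aims 1-3 will be collected in two ways: online or by telephone". The online route is a personal REDCap link. For the telephone route, calls are to be made from a private area, and Section 11 repeats this.
- Section 8 allows collection "in-home, at VNS Health headquarters, at Rutgers University, by phone, by videoconference or online surveys as outlined in the protocol above".

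On use of the results, Section 9 bases feasibility and acceptability on satisfaction ratings, on the percentage of clinicians who find the intervention feasible and acceptable, and on the proportion who report using the materials. On risk, the Aim 3 paragraph of Section 10 says: "For CBPC team members we anticipate no risk".

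**The concern.** The letter names a setting for the staff surveys that the two specific data-collection statements do not include. The setting is a meeting of colleagues at the employer. It is also the kind of meeting used to launch the intervention: under Retention in the Clinical Trial part of Section 5, "we will present the informational materials at interdisciplinary team (IDT) and other team meetings prior to their introduction into clinical practice". Every team member who presents the program is asked to use the materials, so a respondent who did not use them, or disliked them, would be saying so in that setting.

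What is at stake is the credibility of the staff-reported feasibility, acceptability and fidelity results, which are a stated purpose of Aim 3. If some surveys are completed privately and others in meetings, differences between months 1, 3 and 6 could also partly reflect the setting. The plan does not say that the mode of completion will be recorded.

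**Working it through.** **Step 1. What the setting clause refers to.** The letter describes three surveys of 5 to 10 minutes. 3 × 5 = 15 and 3 × 10 = 30 minutes, which reproduces the letter's own total. The surveys account for all the time requested. There is no interview or focus group in this letter to which the meeting option could belong.

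**Step 2. The passages side by side.**

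| Place | Settings or modes for staff surveys | IDT meetings named? |
|---|---|---|
| Section 3, Measurements | Phone or electronic | No |
| Data Collection Protocol | Online or telephone | No |
| Section 8 | Home, headquarters, university, phone, videoconference, online | No |
| Aim 3 letter | Headquarters, IDT meetings, phone, teleconference, electronic | Yes |

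Section 8 covers the headquarters option. It does not name team meetings, and it refers back to the protocol text above it.

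**Step 3. Comparison with the Aim 1 and Aim 2 scripts.** Both telephone scripts also offer IDT meetings to team members, but as a setting for interviews or focus groups. Each then separately limits the questionnaire to a secure or personal link, or the telephone. The Aim 3 letter has the meeting option without that limit. It may be wording carried over from the interview letters; that is an inference.

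**Step 4. Safeguards.** The private-area statement concerns phone calls. Section 11 restricts access to stored data and rules out paper records. Neither says how answers are kept from colleagues while they are being given in a meeting.

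**Step 5. How much one answer weighs.** No staff number is given for Aim 3. The 10 team members in Section 4 are the Aim 1 sample. Take n = 5 to 15 as an assumption.

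- Weight of one respondent in a percentage = 100/n points.
- The satisfaction total runs from 12 to 60 on ratings of 1 to 5, so there are 12 items. If one respondent rates every item one point higher, the mean total moves by 12/n.

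| Assumed n | 100/n (points) | 12/n (mean total) |
|---|---|---|
| 5 | 20.0 | 2.4 |
| 8 | 12.5 | 1.5 |
| 10 | 10.0 | 1.2 |
| 12 | 8.3 | 1.0 |
| 15 | 6.7 | 0.8 |

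These figures show only how sensitive a small survey is. They do not estimate a setting effect, and the documents contain nothing from which one could be estimated.

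**The case against.** The strongest reply is that a setting is not a mode. A clinician who opens a personal link on a phone during a meeting satisfies both the letter and the online-or-telephone rule. The meeting is one option among several, chosen at the respondent's convenience, so anyone uneasy can use the link or a call instead. This stands in part: the conflict can be read away. But the letter does not say that a survey taken in a meeting is completed individually, and the plan nowhere says so either.

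A reader might infer that staff are exposed to identification. The documents do not support that. Nothing says that answers are spoken, shown or collected openly, and Section 11 limits access to authorised study personnel.

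A reader might also infer that the acceptability result is pushed upward. Favourable bias is the plausible direction, but the documents show neither its presence nor its size. The launch presentations at IDT meetings also take place before the materials enter practice, whereas the surveys come 1, 3 and 6 months afterwards. The shared type of meeting is therefore only weak support.

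Finally, the no-risk sentence in Section 10 should not be read alone. The Aims 1-3 paragraph that follows it accepts that confidentiality could be breached, and says that participants may decline questions or stop.

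**Conclusion.** The point holds as an inconsistency with a plausible, unquantified consequence. The letter conflicts with the Measurements paragraph and the Data Collection Protocol, and Section 8 covers it only in part. No safeguard is stated for answers given in a team meeting, so ratings and self-reported non-use obtained there may be biased, probably favourably.

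The importance is moderate. It is confined to the staff-reported measures; the primary endpoint comes from the electronic health record and does not depend on where staff complete surveys. The range of 20 to 6.7 points per respondent rests entirely on the assumed 5 to 15 respondents. That the group is small is suggested by Section 3, which gives team size as one reason for not randomising team members.

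**What to change.** 1. Delete the bracketed IDT-meeting option from the Aim 3 letter. State that each survey is completed individually, by personal REDCap link or by a private call from research staff, as the Data Collection Protocol describes.
2. Align Section 8, and the headquarters and teleconference options left in the letter, with that statement for the Aim 3 staff surveys.
3. Add one sentence to the protocol and the letter: individual answers are not shared with colleagues or CBPC leadership.
4. Optionally, extend the Section 10 sentence on team members to mention confidentiality towards the employer. The general risk is already disclosed there.

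If the sponsor prefers to keep the meeting option, the protocol should say how answers stay private in that setting and record the mode of completion for each survey.

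The cost is a few lines of wording. The links and the telephone follow-up are already planned. The response rate may fall slightly without meeting time set aside, and the telephone follow-up limits that loss.
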